Participants withdrawn from the study agent are those who do not receive the complete number of vaccine doses. A participant withdrawn from the study agent may not necessarily be withdrawn from the study, as further procedures or follow-up may be performed (safety or immunogenicity), if planned in the study protocol. Information relative to premature discontinuation of the study agent will be documented in the CRF. The investigator will document whether the decision to discontinue further vaccination was made by the participant or the investigator and which of the following possible reasons was responsible for withdrawal:

- serious adverse event,
- non-serious adverse event,
- other (specify).

Research Proposal Submission Form for a study involving human subject enrollment WITH specimen collection

Document No.: FTM ECF-033-01

Page 14 of 52

Subjects with positive malaria tests on vaccination days at Month 1 or Month 2 will be treated according to national guidelines and the volunteer will be withdrawn from further vaccination.

B5.6 Indications for deferral of vaccination

The following events constitute contraindications to administration of R21/Matrix-M™ at that point in time. If any one of these adverse events (AEs) occurs at the time scheduled for vaccination, the participant may be vaccinated at a later date, or withdrawn at the discretion of the investigator.

Acute disease at the time of vaccination (acute disease is defined as the presence of a moderate or severe illness with or without fever). All vaccines can be administered to persons with a minor illness such as diarrhoea, mild upper respiratory infection with or without low-grade febrile illness, i.e. Axillary temperature <37.5°C).

- Axillary temperature of $\geq 37.5^{\circ}\text{C}$ at time of vaccination.
- Administration of a vaccine not foreseen by the study protocol within 7 days of any dose of R21/Matrix-M™ with the exception of vaccines against polio, diphtheria, tetanus, pertussis, hepatitis B, Haemophilus influenzae type b (Hib), Bacillus Calmette–Guérin (BCG vaccine), measles, influenza, pneumococcal disease, or yellow fever which may not be given within one week of vaccination.
- COVID-19 vaccines should not be administered 7 days before or after administration of the study vaccine due to potential adverse events e.g. fever.

B5.7 Absolute contraindications to further vaccination

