This study is a randomized, open-label, single centre, Phase 2 trial of R21/Matrix-M™ in healthy Thai adults. A total of 120 participants will be enrolled and randomized into one of three study arms in a ratio of 5:5:2 as described in Section 6.4.4. Each arm will have 50 participants (for arm 1 and 2) and 20 participants (for arm 3).

- For arm 1 and 3, the eligible volunteers will be asked to come into the Hospital for Tropical Diseases to receive the study agents as out-patient on Day 0 (the day of vaccination), Day 1, Day 2, and Day 7 of Study Months 0, 1 and 2; and on Day 0 of Study Months 3 and 6. There are a total of 15 study visits.
- For arm 2, the eligible volunteers will be asked to come into the hospital to receive the study agent (vaccination only) as out-patient on the day of vaccination (Day 0) and Day 7 of Study Months 0, 1 and 2; and on Day 0 of Study Months 3 and 6. There are a total of 9 study visits.

**Research Proposal Submission Form
for a study involving human subject enrollment WITH
specimen collection**

Document No.: FTM ECF-033-01

Page 16 of 52

Table 2. Vaccine and drug administration

Timepoints	Month Day of month	Scr.	Study period														
			M0				M1				M2						
			0	1	2	7	0	1	2	7	0	1	2	7			
Interventions	Vaccination (Group 1 and Group 2)		x					x						x			
	DHA/piperaquine (Group 1 and Group 3)		x	x	x			x	x	x				x	x	x	
	PQ (single low dose primaquine) (Group 1 and Group 3)		x					x						x			

B6.2 Investigational Products:

1) R21/Matrix-M™

Description of Vaccine: The candidate R21 vaccine to be used has been developed by Jenner Institute and manufactured under cGMP conditions at Serum Institute India Private Limited (SIIPL). R21 is produced to high levels in *Hansenula polymorpha* yeast in fermenters. The purified R21 antigen (drug substance) is released after testing, by SIIPL QC Department using qualified and validated methods. The quality released drug substance is used, for manufacturing drug product after appropriately diluting to 20 µg/mL using formulation buffer. The formulated blend is fill finished in siliconized glass vials (4 mL capacity) at a targeted concentration of not less than 20 µg/mL. Each vial is filled with 0.65 mL of the drug product to enable withdrawal of 0.5 mL. The final formulation has 20 mM Tris, 15% sucrose, 30 mM magnesium chloride, pH 7.4.

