The mixing prior to administration strategy will involve withdrawal of 0.5 mL antigen from one vial of R21 Malaria vaccine and adding it to Matrix-M1 vial. 0.5 mL of R21 antigen shall be withdrawn from another vial of R21 Malaria vaccine and be added to the same Matrix-M1 vial. The total volume in Matrix-M1 vial will be 1.5 mL. After addition the content will be mixed gently, and 0.75 mL of the mixture will be withdrawn and administered to participants. Each dose of 0.75mL (after mixing of R21 with Matrix-M1) will contain 10 µg of R21 and 50 µg of Matrix-M1.

Administration of Vaccine: Vaccine preparation will be undertaken under aseptic conditions and in accordance with the trial SOPs. Vaccination administration and vaccine handling will be performed according to the relevant SOPs. The study participants will be observed closely for at least 30 minutes following the administration of study vaccine, with appropriate medical treatment readily available in case of an anaphylactic reaction.

2) Anti-malarial therapy

Participants in Arms 1 and 3 will receive three rounds of antimalarial drugs - each round starting on the day of vaccination (Day 0) at Study Months 0, 1, and 2. Each round consists of three daily doses of co-formulated dihydroartemisinin/piperazine on Day 0, 1, and 2 (i.e. the day of vaccination and each day for 2 days after). Dihydroartemisinin/piperazine tablets (Guilin Pharmaceutical Company or Sigma Tau Pharmaceuticals) for adult patients each contain 40 mg dihydroartemisinin and 320 mg piperazine with a therapeutic dose range between 2–10 mg/kg/day dihydroartemisinin and 16–26 mg/kg/dose piperazine (Table 3). In addition, each participant will receive a single low dose primaquine on the day of vaccination (Day 0) (Table 4). One single low dose primaquine of approximately 0.25 mg/kg (Thai Government Pharmaceutical Organisation) will be administered. This drug regimen has been used in mass drug administrations in more than 10,000 participants which have established that this antimalarial drug regimen is safe and clears gametocytes(15).

In the unexpected event that volunteers are found to be infected with malaria during screening, baseline or during follow-up examination they will be treated according to the most up-to-date government guidelines.

**Research Proposal Submission Form
for a study involving human subject enrollment WITH
specimen collection**

Document No.: FTM ECF-033-01

Page 18 of 52

Table 3. DHA-PIP dosing schedule

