Bodyweight in kilograms	One tablet contains 40mg DHA and 320 mg PIP		
	Number of tablets/day	Total tablets/month	Total tablets/study
≤ 50.0	2.5	7.5	22.5
> 50.0 to ≤ 60.0	3	9	27.0
> 60.0 to ≤ 70.0	3.5	10.5	31.5
> 70.0 to ≤ 85.0	4	12	36.0
> 85.0	5	15	45.0

Table 4. Primaquine dosing schedule

Bodyweight in kilograms	One tablet contains 15mg primaquine		
	Number of tablets/day	Total tablets/month	Total tablets/study
≤ 50.0	0.5	0.5	1.5
> 50.0 to ≤ 60.0	1.0	1.0	3.0
> 60.0 to ≤ 70.0	1.0	1.0	3.0
> 70.0 to ≤ 85.0	1.5	1.5	4.5
> 85.0	2.0	2.0	6.0

If the vomiting occurs within 30 minutes after the drug administration, the entire dose will be re-administered.

If the vomiting occurred between 30 and 60 minutes after the drug administration, the half dose will be re-administered.

In case the 2nd vomiting occur, the “administration of further study drug doses is left to the discretion of the treating physician if the patient wants to try again.

B6.2.1 Storage of vaccines and anti-malarial medications

The R21 vaccine antigen and Matrix-M adjuvant must be stored according to the manufacturer’s recommendations at +2°C to +8°C. Any temperature excursions outside the range +2°C to 8°C must be reported to the Jenner Institute and SIPL as soon as detected. Following an exposure to such a temperature deviation, vaccines will not be used until approval has been given by the study PI in consultation with Jenner Institute and SIPL. Study anti-malarial medications must be stored at room temperature below 30 degrees Celsius. All vaccines and study medications will be stored in a safe and locked place, with no access to unauthorized personnel. Only trained, authorized study staff will have access to the vaccines and study medications. Storage temperatures will be monitored daily, according to standard operating procedures (SOPs) at the investigator’s site. In addition, for vaccine storage refrigerator(s), an alarm system and a back-up refrigerator will be available in case of power failure/breakdown. All movements of the study vaccines will be documented and cold boxes, with temperature monitoring, will be used to transfer vaccines to the area where it will be administered.

**Research Proposal Submission Form
for a study involving human subject enrollment WITH
specimen collection**

Document No.: FTM ECF-033-01

Page 19 of 52

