Vaccine and study medication accountability, storage, and handling will be in accordance with local SOPs. This study will not be blinded; i.e. it is an open-label study.

B6.2.2 Accountability of the study agents

The study site will maintain a record of the numbers of all vaccines and DHA/PIP + primaquine tablets obtained, used by the participants and returned to the pharmacy room in CTU. On study completion, a copy of the drug accountability record will be filed in the study folder.

B6.2.3 Concomitant medications

There will be no restrictions on concomitant medication beyond the exclusion criteria listed above.

B6.3 Study Endpoints

B6.3.1 Primary Endpoints

The safety of the investigational vaccine in each group:

- Occurrence of solicited from the date of each vaccination to 7 days of each vaccination.
- Occurrence of unsolicited adverse events (AEs) from the date of the first vaccination to 28 days after the last vaccination, according to the MedDRA classification.
- Occurrence of serious adverse events (SAEs) during the whole study period, i.e. during a 6-month follow up period from the receipt of first vaccination, according to the MedDRA classification.

B6.3.2 Secondary Endpoints

- For Arms 1 and 2, the concentration of antibodies against *Plasmodium falciparum* circumsporozoite (anti-NANP total IgG antibody), one month after the first dose (at Study month 1), one month after the second dose (at Study month 2), one month after the third dose (at Study Month 3) and six months after the first dose (at Study Month 6).
- Exploratory immunology endpoints including but not limited to cellular immunity.
- For Arms 1 and 3, piperaquine levels following the administration of the antimalarials with or without vaccine. (timepoints)

B6.4 Details of procedures for specimen/data collection

Procedures will be performed at the time points indicated in the schedule of procedures (Table 5). Additional procedures or laboratory tests may be performed, at the discretion of the investigators if clinically necessary (e.g. follow up repeat haematology or biochemistry laboratory tests in the event of clinically significant abnormal results).

Research Proposal Submission Form for a study involving human subject enrollment WITH specimen collection

Document No.: FTM ECF-033-01

Page 20 of 52

Table 5. Study Procedures

Timepoints	Month Day of month	Scr.	Study period																	
			M0				M1				M2				M3	M6 ^a				
			0 ^c	1	2	7	0	1	2	7	0	1	2	7	0	0				

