specimen collection**

Document No.: FTM ECF-033-01

Page 29 of 52

The investigators will permit authorized representatives of the sponsor, ethical committee(s), regulatory agencies, authorized individuals from, Jenner Institute and the monitors to examine (and when required by applicable law, to copy) clinical records for the purposes of quality assurance reviews, audits and evaluation of the study safety and progress.

B6.7 Data analysis

B6.7.1 Study Endpoints

We will assess the R21/Matrix-M™ recipients with regards to:

Safety: the occurrence of solicited and unsolicited AEs and SAEs (please see safety section)

Immunogenicity: (a) serum anti-CS IgG antibody titres responses to NANP and anti-CS antibody avidity, (b) cellular immunity.

B6.7.2 Inclusion in Analysis

All patients who received at least one dose of vaccine will be included in the safety analyses. Patients lost to follow-up before the completion of the follow-up period assessments will be censored at the last day seen.

B6.7.3 Immunology analyses

Given the incidence of malaria in the study area, it is highly unlikely that any volunteer will become infected with any Plasmodium species during the trial. However, to exclude the remote possibility that a participant becomes infected we will screen participants for malaria at screening, Month 0, Month 1, Month 2, Month 3, and Month 6. Participants positive for malaria at screening or Month 0 are excluded from participation in the study and will not be enrolled or vaccinated.

B6.7.4 Overall plan

Both intention-to-treat and per-protocol analyses will be carried out. In the intention-to-treat analysis, every participant randomized in the study (who receive the correct or incorrect study agent, one or more doses, and complete or incomplete doses) will be analysed, except if he/she did not receive any dose of the study vaccine or if no post-randomization data was collected for this participant.

The per-protocol analysis will compare participants according to the study agent actually received and will include only those participants who satisfied the inclusion/exclusion criteria, followed the protocol, and received three complete, correct doses. The following non-compliant participants will be excluded:

- Participants included without meeting at least one inclusion criterion
- Participants included despite meeting at least one exclusion criterion
- Participants found non-compliant with the blood sampling schedule

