1.4 Detecting and recording adverse events and serious adverse events

1.4.1 Recording adverse events, serious adverse events and pregnancies

All AEs must be recorded into the appropriate section of the CRF, irrespective of intensity or whether or not they are considered vaccination-related.

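### The safety and ITT populations and the discontinuation row are defined by vaccine receipt alone, so Arm 3 and antimalarial-only stops fall outside them

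*Protocol*

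**What the plan says.** **Populations.** Protocol B6.7.2 gives the safety rule, and SAP 3.1 repeats it: "All patients who received at least one dose of vaccine will be included in the safety analyses". SAP section 5 opens with a different restriction, to participants allocated to vaccination. SAP 4.1.4 makes the safety outcomes ITT. The ITT rule, the same in Protocol B6.7.4 and SAP 4.1.4, takes everyone randomised except those with no dose of the study vaccine or no post-randomisation data.

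**Discontinuation.** Protocol B5.5 says "Participants withdrawn from the study agent are those who do not receive the complete number of vaccine doses". The recorded decision-maker and reason belong to stopping the vaccine: "The investigator will document whether the decision to discontinue further vaccination was made by the participant or the investigator". The only planned output on AE-driven discontinuation is withdrawal from further vaccination. It appears in Protocol Appendix B 1.6 and in the list and Table 4 of SAP section 5.

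**What counts as a study agent.** Elsewhere the term includes the antimalarials. In B6.1, participants in Arms 1 and 3 "will be asked to come into the Hospital for Tropical Diseases to receive the study agents as out-patient". B6.2.2, on accountability of the study agents, says "The study site will maintain a record of the numbers of all vaccines and DHA/PIP + primaquine tablets obtained".

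**What is to be reported.** The SAP 3.2 primary outcome is the safety of the investigational treatment in each group, with antibody concentrations for all three groups. SAP Table 4 has a No Vaccine column, and the immunogenicity tables have a No vaccine row.

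**The concern.** The rules for entering the analysis and the tables to be filled do not agree. Arm 3 is never vaccinated, so a vaccine-dose criterion removes it entirely, yet the tables reserve a place for it.

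Arm 3 matters for reading the safety results. Protocol Appendix B 1.5.2 accepts that, when vaccine and antimalarials are given together, it may be impossible to attribute a general AE to one or the other. Protocol C2.1 lists nausea, vomiting, diarrhoea and headache among the main DHA-PIP side effects, and all four are also solicited AEs. Arm 3 is the only group that shows how often such events occur on the drugs without vaccine. If a programmer applies the written rule, that column is empty. If not, someone has to choose a population after the open-label data have accrued.

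The discontinuation row has the same fault on a smaller scale. It says nothing about how many people gave up the antimalarials because of an AE, which is a basic tolerability figure for a vaccine meant to accompany mass drug administration.

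**Working it through.** **1. Who enters each set.** Inputs: 120 participants randomised 5:5:2 (Protocol B6.1); Arm 3 receives no vaccine (Protocol B5.3, Table 1).

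Arms 1 and 2: 120 × 5/12 = 50 each. Arm 3: 120 × 2/12 = 20.

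| Rule | Criterion | Arm 3 treated as allocated |
|---|---|---|
| Safety: B6.7.2, SAP 3.1 | at least one vaccine dose | 0 of 20 enter |
| Safety: SAP section 5 | allocated to vaccination | 0 of 20 enter |
| ITT: B6.7.4, SAP 4.1.4 | not excluded for lack of a vaccine dose | 0 of 20 enter |
| Per protocol: B6.7.4, SAP 4.1.4 | not excluded from ITT | 0 of 20 enter |

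The last line follows because both documents list exclusion from the ITT analysis as a per-protocol exclusion. SAP 4.1.4 makes per protocol the main strategy for immunogenicity, so the literal rule also empties the No vaccine rows of the immunogenicity tables. The loss is 20/120 = 16.7% of the trial and 20/70 = 28.6% of those given antimalarials.

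**2. What the discontinuation row can count.**
- Arm 3: withdrawal from further vaccination cannot occur, so the cell carries no information even if the arm is restored.
- Arm 1: a participant who stops only the antimalarials still has a complete vaccine course under B5.5 and is not counted.
- Arm 1 after Month 2 Day 0: the third vaccine dose has been given, so a drug stop on Day 1 or Day 2 cannot meet the definition at all.

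**3. Scheduled exposure.** DHA-PIP is given daily for 3 days in each of 3 rounds (Protocol B6.2), so 9 daily doses per person. Primaquine is given once per round, so 3.
- DHA-PIP: 50 × 9 = 450 (Arm 1) + 20 × 9 = 180 (Arm 3) = 630.
- Primaquine: 50 × 3 + 20 × 3 = 210.
- Vaccine: 100 × 3 = 300.
- Arm 1 DHA-PIP doses after the third vaccine dose: 50 × 2 = 100, and 100/450 = 22%.

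These are scheduled doses, not events. The documents give no discontinuation rate, so the number of uncounted stops cannot be estimated.

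**4. Precision of the new row.** The exact two-sided 95% upper limit with zero events is 1 − 0.025^(1/n).
- n = 50: 1 − 0.025^(1/50) = 7.1%.
- n = 20: 1 − 0.025^(1/20) = 16.8%.

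**5. Power.** Full enumeration of the two-sided Fisher's exact test for 50% versus 80%, 50 per arm, 5% level, gives 85.3%, matching the stated 85%. It concerns Arms 1 and 2 only and is not affected.

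**The case against.** **The objective is vaccine safety.** The primary objective, and the endpoint in Protocol B6.3.1, concern the vaccine, and the protocol treats the drug regimen as well established. Tabulating vaccine discontinuation is coherent with that. This stands as a reason to call the extra row optional. It does not explain populations that exclude an arm which the SAP's own tables report.

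**Capture elsewhere.** SAP 4.1.4 requires complete, correct doses of the agent or treatment received. An incomplete antimalarial course may therefore be a per-protocol exclusion, with its reason in the SAP 4.1.3 flowchart. Tablets are counted under B6.2.2. The CRF is not among the documents and may already hold a drug-stop item. All this stands as partial capture, but none of it is a safety output, and someone who stops tablets and stays in follow-up need not appear as a drop-out.

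**The population change is a separate matter.** It is distinct, and it is the more important half. Without it the Arm 3 cell of any new row stays outside the safety set.

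**Stronger readings that the documents do not support.**
- A reader might infer that Arm 3 safety data are lost. They are not: Appendix B 1.4.1 says "All AEs must be recorded into the appropriate section of the CRF, irrespective of intensity", and B6.4.5 gives every participant a diary card.
- A reader might take the vomiting text in B6.2 as a foreseen drug discontinuation: "administration of further study drug doses is left to the discretion of the treating physician if the patient wants to try again". It follows instructions on repeating a vomited dose and is most naturally about re-dosing.
- A reader might take the and/or wording on vaccine and drug in Appendix B 1.7 as proof that drugs are to be stopped while vaccination continues. It may only reflect one rule serving three arms.

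**Conclusion.** The population rules are wrong as written. On a literal reading they remove all 20 Arm 3 participants from the safety and ITT sets, against SAP 3.2 and the No Vaccine entries in the tables. The tables make it likely that Arm 3 was meant to be included, so this is a drafting fault to settle before the analysis and not evidence of an intention to drop the arm.

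The discontinuation row is a smaller matter. It cannot apply to Arm 3 and cannot count an antimalarial-only stop in Arm 1. What is missing is the count of such stops by arm; the AEs behind them are still recorded with causality. The size of that gap is unknown, because no stop rate is given. No test, sample size or power figure changes.

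The conclusion assumes that Arm 3 participants are treated as allocated. Under B6.7.2, SAP 3.1 and the ITT rule, one vaccinated in error would not be excluded for lack of a vaccine dose.

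**What to change.** 1. In Protocol B6.7.2, SAP 3.1 and the opening of SAP section 5, use one safety population: participants who received at least one dose of any study agent, vaccine or antimalarial.
2. In the ITT rule (Protocol B6.7.4, SAP 4.1.4), replace *study vaccine* with *study agent*. This also returns Arm 3 to the per-protocol set and to the immunogenicity tables. In Arm 1 it would admit anyone who took antimalarials but no vaccine; such cases should be listed.
3. In Appendix B 1.6 and in the list and Table 4 of SAP section 5, split the row: AEs/SAEs leading to withdrawal from vaccination (Arms 1 and 2; Arm 3 not applicable), and from antimalarials (Arms 1 and 3; Arm 2 not applicable).
4. In B5.5, define discontinuation separately for vaccine and antimalarials, with date, decision-maker and reason for each.
5. Because the AE windows run from vaccination, state that in Arm 3 they run from Day 0 of each antimalarial round.

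The cost is wording in these sections, one descriptive row, and one CRF item if it is not already there. Item 2 is more than editorial, since the ITT rule also governs immunogenicity. The new row will have wide intervals and will not support a firm comparison of Arm 1 with Arm 3.
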